12.10 Events of Clinical Interest for Pembrolizumab

Selected non-serious and serious AEs are also known as Events of Clinical Interest and must be reported to Redx Pharma within 24 hours of awareness.

Events of Clinical Interest for this study include:

1. An overdose of pembrolizumab, as defined in Section 8.4, that is not associated with clinical symptoms or abnormal laboratory results.
2. An elevated AST or ALT laboratory value that is greater than or equal to $3 \times$ the ULN and an elevated total bilirubin laboratory value that is greater than or equal to $2 \times$ the ULN and, at the same time, an alkaline phosphatase laboratory test value that is less than $2 \times$ the ULN, as determined by way of protocol-specified laboratory testing or unscheduled laboratory testing.*

*Note: These criteria are based upon available regulatory guidance documents. The purpose of the criteria is to specify a threshold of abnormal hepatic tests that may require additional evaluation for an underlying aetiology. The trial site guidance for assessment and follow up of these criteria can be made available. It may also be appropriate to conduct additional evaluation for an underlying aetiology in the setting of abnormalities of liver blood tests including AST, ALT, bilirubin, and alkaline phosphatase that do not meet the criteria noted above. In these cases, the decision to proceed with additional evaluation will be made through consultation between the study investigators and the Sponsor Medical Monitor. However, abnormalities of liver blood tests that do not meet the criteria noted above are not Events of Clinical Interest for this trial.

12.11 Statistical Considerations

General statistical considerations can be found in Section 9.

12.11.1 Module 3 Sample Size Determination

The method by Frewer et al (Frewer et al 2016), together with the totality of the data collected, will be used to guide go/no-go decision making.

In the KEYNOTE-158 and KEYNOTE-028 studies, a combined response rate of approximately 10% has been observed (Piha-Paul et al 2020), thus an improvement to CCI% would be clinically significant and is used as the CCI in setting the go/no-go hurdles in terms of an efficacy rate that would not want to be missed. CCI

CCI If response is seen in CCI or fewer patients, then there is less than a CCI% probability that the true ORR rate is greater than the CCI. These hurdles will be used to guide

the decision for onward development. The totality of the data, including the population enrolled and the results from the secondary endpoints will be used for the final decision.

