2.2.4.4 Clinical Trials of Pembrolizumab in Patients with Biliary Tract Cancer

Pembrolizumab has demonstrated anti-tumour activity in patients with advanced BTC who had no other options for standard therapy, in 2 clinical studies (KEYNOTE-028 and KEYNOTE-158) (Piha-Paul et al 2020). The primary efficacy endpoint for each study was ORR by RECIST v1.1. The Phase 1b KEYNOTE-028 study enrolled 24 patients; median follow-up was 5.7 months. The ORR was 13.0% (3/23; 95% CI: 2.8%-33.6%); median DOR was not reached (range, 21.5-53.2+ months). Median (95% CI) OS and PFS were 5.7 (3.1-9.8) and 1.8 (1.4-3.1) months. The Phase 2 KEYNOTE-158 study enrolled 104 patients; median follow-up was 7.5 months. In KEYNOTE-158, ORR was 5.8% (6/104; 95% CI, 2.1%-12.1%); median DOR was not reached (range, 6.2-26.6+ months). Median (95% CI) OS and PFS were 7.4 (5.5-9.6) and 2.0 (1.9-2.1) months. The safety profile of pembrolizumab in patients with BTC in these 2 studies was manageable, and no new safety signals were identified. Pembrolizumab is currently being investigated, in combination with standard cisplatin and gemcitabine chemotherapy, as a first-line treatment option for patients with advanced or unresectable BTC in a Phase 3 study, KEYNOTE-966 (NCT04003636).

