9.1 Statistical Hypotheses

The statistical hypotheses for testing the activity of RXC004 in Module 1 (pancreatic cancer), and Modules 2 and 3 (biliary tract cancer) independently are:

$$H_0 : p \leq p_0$$

$$H_1 : p \geq p_1$$

Where H_0 is the null hypothesis, p is the observed response rate, p_0 is the response rate for available treatment options – CCI, H_1 is the alternative hypothesis and p_1 is the target response rate – CCI.

The primary summary measure for Module 1 and Module 2 is the progression free survival rate at 6 months. For module 1 the corresponding p_0 and p_1 are CCI% and CCI%. For Module 2 the corresponding p_0 and p_1 are CCI% and CCI%. The primary summary measure for Module 3 is the objective response rate. For Module 3 the corresponding p_0 and p_1 are CCI% and CCI%.

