12.5.1 Rationale for Primary Endpoint

The combination of RXC004 with pembrolizumab is expected to result in both a RXC004-based effect on tumour cell growth and a synergistic effect with pembrolizumab on the immune system. RXC004 should reverse Wnt pathway-induced immune evasion and pembrolizumab will allow activated CD8 T cells to function without the immune suppression resulting from tumour PD-L1 expression. Therefore, it is anticipated that with combination therapy, the active CD8 T cells will destroy tumour cells and shrink the size of the tumour; hence, ORR is considered to be an appropriate primary endpoint for Module 3.

Furthermore, ORR was selected as the primary endpoint for the pembrolizumab single-arm monotherapy studies KEYNOTE-028 and KEYNOTE-158 in patients with advanced BTC (Piha-Paul et al 2020), and responses have been observed in these studies with an ORR of 13.0% (3/23) and 5.8% (6/104), respectively. Therefore, improving this ORR is considered an appropriate primary objective, with these studies providing an objective benchmark.

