**CCI**

CCI

CCI

If [REDACTED] or less are progression free at 6 months RXC004 would be determined not worthy of further investigation with this patient population. The type I and II error rates associated with this testing are 0.06 and 0.20, respectively. The PFS at 6 months rate will be used to guide the decision for onward development. The totality of the data, including the results from the secondary endpoints will be used to in the final decision.

Approximately CCI patients are expected to be enrolled in order for CCI patients to be evaluable.

### Module 3

In the KEYNOTE-158 and KEYNOTE-028 studies, a combined response rate of approximately CCI% has been observed (Piha-Paul et al 2020), thus an improvement to CCI% would be clinically significant and is used as the CCI in setting the go/no-go hurdles in terms of an efficacy rate that would not want to be missed. CCI

CCI

CCI

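### Module 3 benchmark: Protocol 12.11.1 reports a combined KEYNOTE response rate of about 10%, but the protocol's own counts pool to 9/127 = 7.1%

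*Protocol*

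**What the plan says.** Protocol 2.2.4.4 reports the two pembrolizumab monotherapy studies with counts and exact intervals. Protocol 12.5.1 repeats the ORRs as "13.0% (3/23) and 5.8% (6/104), respectively", in the order KEYNOTE-028, KEYNOTE-158. It makes improving on that ORR the aim of Module 3, "with these studies providing an objective benchmark".

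Protocol 12.11.1 then states that in these two studies "a combined response rate of approximately 10% has been observed". From that it derives a higher ORR (redacted) that would be clinically significant, and uses the higher ORR "in setting the go/no-go hurdles in terms of an efficacy rate that would not want to be missed". It does not say how the two studies were combined.

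Protocol 9.1 specifies a p0 and a p1 for each module, where p0 "is the response rate for available treatment options"; the Module 3 values are redacted. SAP 4.15 carries the same Module 3 sentence, beginning "In the KEYNOTE-158 and KEYNOTE-028 studies, a combined response rate of approximately", with the percentage redacted.

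**The concern.** The three protocol sections describe the same two studies, yet the combined rate does not follow from the counts. KEYNOTE-158 supplies 104 of the 127 patients and had an ORR of 5.8%, so any weighting that respects study size must land much nearer 5.8% than 13.0%.

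The number matters because Module 3 has no control arm. These two studies are its only stated benchmark for the primary endpoint, and 12.11.1 reasons directly from 10% to the ORR worth detecting. A reader of the final result will measure improvement from 10% when the cited data put the starting point near 7%. If 10% is also the lower reference behind a go rule, that rule asks for more responses than the cited data would require.

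**Working it through.** **Inputs** (Protocol 2.2.4.4; the counts are repeated in 12.5.1)

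| Study | Responders / patients | ORR | 95% CI in protocol | Exact (Clopper-Pearson) 95% CI, recomputed |
|---|---|---|---|---|
| KEYNOTE-028 | 3/23 | 13.0% | 2.8% to 33.6% | 2.8% to 33.6% |
| KEYNOTE-158 | 6/104 | 5.8% | 2.1% to 12.1% | 2.1% to 12.1% |

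The per-study figures reproduce exactly, so the counts are sound and the problem lies in the combining.

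**Pooled rate.** (3 + 6)/(23 + 104) = 9/127 = 7.09%, exact 95% CI 3.29% to 13.03%. Using the 24 patients enrolled in KEYNOTE-028 as its denominator gives 9/128 = 7.0%.

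**Can another method give 10%?**

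| Method | Combined ORR |
|---|---|
| Inverse variance, raw scale | 6.5% |
| Simple pooling | 7.1% |
| Inverse variance, logit scale | 7.5% |
| Random effects (DerSimonian-Laird), logit scale | 7.9% |
| Weights proportional to square root of n | 8.1% |
| Unweighted mean, (13.04 + 5.77)/2 | 9.4% |

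None reaches 10%. The weight on KEYNOTE-028 that would give 10% is (10 − 5.77)/(13.04 − 5.77) = 58.2%. Its share of the patients is 23/127 = 18.1%.

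**Size of the gap.** 10 − 7.09 = 2.91 percentage points. In patients, 0.10 × 127 = 12.7, about 13 responders, against 9 observed. For any target ORR T, the improvement over the pooled rate is T − 7.09 rather than T − 10, so it is 2.91 points larger than the text implies, whatever T is.

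**Possible effect on a go cut-off (illustration only).** The real N, error rates and rule are redacted. Assume that 10% is the lower reference and that the go cut-off is the smallest r with P(X ≥ r | N, p0) ≤ alpha. Take N = 15 to 40 (26 values) and alpha = 0.05 to 0.20 in steps of 0.01 (16 values), which makes 26 × 16 = 416 combinations. Compare p0 = 0.10 with p0 = 9/127:

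| Extra responders required with 10% | Combinations |
|---|---|
| 0 | 28 |
| 1 | 323 |
| 2 | 65 |

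So the cut-off is higher in 323 + 65 = 388 of 416. For fixed cut-offs under the same assumptions, the chance of at least r responses at a true rate of 10% versus 7.1% is:

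| N | r | 10% | 7.1% |
|---|---|---|---|
| 20 | 4 | 0.133 | 0.049 |
| 25 | 5 | 0.098 | 0.029 |
| 30 | 6 | 0.073 | 0.017 |

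**The case against.** The strongest reply has five parts.

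- **The wording is approximate and 10% is not excluded.** It lies inside the pooled interval, and the unweighted mean of 9.4% is a plausible origin; measured from that, the gap to 7.1% is 9.41 − 7.09 = 2.3 points. This supports 10% as a permissible planning value. It does not make 10% the rate the two studies observed, which is what 12.11.1 says.
- **The direction is probably conservative.** If 10% is the lower reference, a false go becomes less likely. That stands, and the cost would fall on the other side, as a stricter go hurdle for an active combination.
- **The visible Module 3 rule is not the one in the illustration.** The text gives no explicit test or error rates for this module, unlike Modules 1 and 2. The higher target, not the 10%, is what is said to enter the hurdles. If the redacted reference in the no-go sentence is that target, the no-go cut-off does not change once the target is fixed. The target may also have been chosen as an absolute rate. This stands too: the grid shows what could happen, not what did.
- **The decision does not rest on the hurdles alone.** Section 12.11.1 says they guide it, alongside all the other data. That limits the consequence but leaves the figure uncorrected.
- **Simple pooling of a Phase 1b and a Phase 2 study is one choice among several.** True, but every method that gives the larger study more weight returns 6.5% to 8.1%.

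**Conclusion.** The concern holds. The protocol's counts give a combined ORR of 7.1% (9/127; exact 95% CI 3.3% to 13.0%), and the figure of about 10% in 12.11.1 is wrong as a statement of what was observed. The gap of about 2.9 points follows from the documents alone, with no assumption beyond patient-level pooling.

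It is more than a background slip, because 12.11.1 argues from this number to the clinically significant ORR for a single-arm primary endpoint. It is not, however, a demonstrated error in the decision rule. The Module 3 p0, p1, sample size, error rates and cut-offs are redacted, so whether any hurdle moves cannot be determined from the public text. Only if 10% is the lower reference would the go hurdle be too strict; under the assumed exact rule this would typically be by one responder. The correction should be made, and the sponsor, who holds the redacted values, can settle the consequence directly.

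**What to change.** In Protocol 12.11.1, give the combined ORR as 7.1% (9/127; exact 95% CI 3.3% to 13.0%) and say that it is the pooled proportion. Check that the unredacted figure in SAP 4.15 agrees. Then re-check the clinically significant ORR and the go/no-go hurdles against 7.1%, and record whether either changes.

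If the intention was to plan against 10%, say that it is a deliberately conservative reference set above the observed 7.1%, and report the hurdles' operating characteristics at both rates.

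The cost is a change of wording and a short recalculation, with no extra patients and no new data.

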13 APPENDICES

Appendix A Regulatory, Ethical, and Study Oversight Considerations

A 1 Regulatory and Ethical Considerations

- This study will be conducted in accordance with the protocol and with the following:
 - Consensus ethical principles derived from international guidelines including the Declaration of Helsinki and Council for International Organizations of Medical Sciences (CIOMS) International Ethical Guidelines
 - Applicable ICH Good Clinical Practice (GCP) Guidelines
 - Applicable laws and regulations.
- The protocol, protocol amendments, ICF, Investigator Brochure, and other relevant documents (e.g., advertisements) must be submitted to an IRB/IEC by the investigator and reviewed and approved by the IRB/IEC before the study is initiated.
- Any amendments to the protocol will require IRB/IEC and applicable Regulatory Authority approval before implementation of changes made to the study design, except for changes necessary to eliminate an immediate hazard to study participants.
- Redx will be responsible for obtaining the required authorisations to conduct the study from the concerned Regulatory Authority. This responsibility may be delegated to a CRO but the accountability remains with Redx.

Regulatory Reporting Requirements for SAEs

- Prompt notification by the investigator to the sponsor of a SAE is essential so that legal obligations and ethical responsibilities towards the safety of participants and the safety of a study intervention under clinical investigation are met.
- The sponsor has a legal responsibility to notify both the local regulatory authority and other regulatory agencies about the safety of a study intervention under clinical investigation. The sponsor will comply with country-specific regulatory requirements relating to safety reporting to the regulatory authority, Institutional Review Boards (IRB)/Independent Ethics Committees (IEC), and investigators.
- For all studies except those utilising medical devices investigator safety reports must be prepared for suspected unexpected serious adverse reactions (SUSAR) according to local regulatory requirements and sponsor policy and forwarded to investigators as necessary.
- An investigator who receives an investigator safety report describing a SAE or other specific safety information (e.g. summary or listing of SAEs) from the sponsor will review and then file it along with the Investigator's Brochure and will notify the IRB/IEC, if appropriate according to local requirements.

A 2 Financial Disclosure

Investigators and sub-investigators will provide the sponsor with sufficient, accurate financial information as requested to allow the sponsor to submit complete and accurate financial certification or disclosure statements to the appropriate regulatory authorities. Investigators are responsible for providing information on financial interests, which includes any changes to financial interests throughout and also after the study has concluded.

A 3 Informed Consent Process

- The investigator or his/her representative will explain the nature of the study to the patient or his/her legally authorised representative and answer all questions regarding the study.
- Patients must be informed that their participation is voluntary and they are free to refuse to participate and may withdraw their consent at any time and for any reason during the study. Patients or their legally authorised representative will be required to sign a statement of informed consent that meets the requirements of 21 CFR 50, local regulations, ICH guidelines, Health Insurance Portability and Accountability Act (HIPAA) requirements, where applicable, and the IRB/IEC or study centre.
- The medical record must include a statement that written informed consent was obtained before the patient was enrolled in the study and the date the written consent was obtained. The authorised person obtaining the informed consent must also sign the ICF.
- Patients must be re-consented to the most current version of the ICF(s) during their participation in the study.
- A copy of the ICF(s) must be provided to the participant or the participant's legally authorised representative.

The ICF will contain a separate section that addresses and documents the collection and use of any mandatory and/or optional human biological samples. The investigator or authorised designee will explain to each participant the objectives of the analysis to be done on the samples and any potential future use. Participants will be told that they are free to refuse to participate in any optional samples or the future use and may withdraw their consent at any time and for any reason during the retention period.

A 4 Data Protection

- Patients will be assigned a unique identifier by the sponsor. Any patient records or datasets that are transferred to the sponsor will contain the identifier only; patient names or any information which would make the patient identifiable will not be transferred.
- The patient must be informed that his/her personal study-related data will be used by the sponsor in accordance with local data protection law. The level of disclosure and use of their data must also be explained to the patient in the informed consent.

- The patient must be informed that his/her medical records may be examined by Clinical Quality Assurance auditors or other authorised personnel appointed by the sponsor, by appropriate IRB/IEC members, and by inspectors from regulatory authorities.

A 5 Dissemination of Clinical Study Data

A description of this clinical study will be available on <http://www.clinicaltrials.gov>, as will the summary of the main study results when they are available. The clinical study and/or summary of main study results may also be available on other websites according to the regulations of the countries in which the study is conducted.

A 6 Data Quality Assurance

- All patient data relating to the study will be recorded on eCRF unless transmitted to the sponsor or designee electronically (e.g. laboratory data). The investigator is responsible for verifying that data entries are accurate and correct by physically or electronically signing the eCRF.
- The investigator must maintain accurate documentation (source data) that supports the information entered in the eCRF.
- The investigator must permit study-related monitoring, audits, IRB/IEC review, and regulatory agency inspections and provide direct access to source data documents.
- The sponsor or designee is responsible for the data management of this study including quality checking of the data.
- The sponsor assumes accountability for actions delegated to other individuals (e.g. Contract Research Organizations).
- Study monitors will perform ongoing source data verification to confirm that data entered into the eCRF by authorised site personnel are accurate, complete, and verifiable from source documents; that the safety and rights of patients are being protected; and that the study is being conducted in accordance with the currently approved protocol and any other study agreements, ICH GCP, and all applicable regulatory requirements.

Records and documents, including signed ICFs, pertaining to the conduct of this study must be retained by the investigator for 2 years after the last marketing application unless local regulations or institutional policies require a longer retention period. No records may be destroyed during the retention period without the written approval of the sponsor. No records may be transferred to another location or party without written notification to the sponsor.

A 7 Source Documents

- Source documents provide evidence for the existence of the patient and substantiate the integrity of the data collected. Source documents are filed at the investigator's site.

- Data reported on the eCRF or entered in the eCRF that are transcribed from source documents must be consistent with the source documents or the discrepancies must be explained. The investigator may need to request previous medical records or transfer records, depending on the study. Also, current medical records must be available.

A 8 Study and Site Start and Closure

The study start date is the date on which the clinical study will be open for recruitment of patients.

The first act of recruitment is the first site open and will be the study start date.

The sponsor designee reserves the right to close the study site or terminate the study at any time for any reason at the sole discretion of the sponsor. Study sites will be closed upon study completion. A study site is considered closed when all required documents and study supplies have been collected and a study-site closure visit has been performed.

The investigator may initiate study-site closure at any time, provided there is reasonable cause and sufficient notice is given in advance of the intended termination.

Reasons for the early closure of a study site by the sponsor or investigator may include but are not limited to:

- Failure of the investigator to comply with the protocol, the requirements of the IRB/IEC or local health authorities, the sponsor's procedures, or GCP guidelines
- Inadequate recruitment of participants by the investigator
- Discontinuation of further study intervention development

If the study is prematurely terminated or suspended, the sponsor shall promptly inform the investigators, the IECs/IRBs, the regulatory authorities, and any contract research organization(s) used in the study of the reason for termination or suspension, as specified by the applicable regulatory requirements. The investigator shall promptly inform the participant and should assure appropriate participant therapy and/or follow-up.

A 9 Publication Policy

- The data generated by this study are confidential information of the Sponsor. The Sponsor will make the results of the study publicly available. The publication policy with respect to the Investigator and study centre will be set forth in the Clinical Trial Agreement.
- The sponsor will comply with the requirements for publication of study results. In accordance with standard editorial and ethical practice, the sponsor will generally support

publication of multicentre studies only in their entirety and not as individual site data. In this case, a coordinating investigator will be designated by mutual agreement.

Appendix B Adverse Events: Definitions and Procedures for Recording, Evaluating, Follow-up, and Reporting

B 1 Definition of Adverse Events

An adverse event is the development of any untoward medical occurrence in a patient or clinical study participant administered a medicinal product and which does not necessarily have a causal relationship with this treatment. An AE can therefore be any unfavourable and unintended sign (e.g. an abnormal laboratory finding), symptom (for example nausea, chest pain), or disease temporally associated with the use of a medicinal product, whether or not considered related to the medicinal product.

The term AE is used to include both serious and non-serious AEs and can include a deterioration of a pre-existing medical occurrence. An AE may occur at any time, including run-in or washout periods, even if no Study treatment has been administered.

B 2 Definitions of Serious Adverse Event

A serious adverse event is an AE occurring during any study phase (i.e. run-in, treatment, washout, follow-up), that fulfils one or more of the following criteria:

- Results in death
- Is immediately life-threatening
- Requires in-participant hospitalisation or prolongation of existing hospitalisation
- Results in persistent or significant disability or incapacity
- Is a congenital abnormality or birth defect
- Is an important medical event that may jeopardise the participant or may require medical treatment to prevent one of the outcomes listed above.

Adverse Events (AEs) for **malignant tumours** reported during a study should generally be assessed as **Serious** AEs. If no other seriousness criteria apply, the 'Important Medical Event' criterion should be used. In certain situations, however, medical judgement on an individual event basis should be applied to clarify that the malignant tumour event should be assessed and reported as a **Non-Serious** AE. For example, if the tumour is included as medical history and progression occurs during the study, but the progression does not change treatment and/or prognosis of the malignant tumour, the AE may not fulfil the attributes for being assessed as Serious, although reporting of the progression of the malignant tumour as an AE is valid and should occur. Also, some types of malignant tumours, which do not spread remotely after a routine treatment that does not require hospitalization, may be assessed as Non-Serious; examples in adults include Stage 1 basal cell carcinoma and Stage 1A1 cervical cancer removed via cone biopsy.

The above instruction applies only when the malignant tumour event in question is a new malignant tumour (i.e., it is **not** the tumour for which entry into the study is a criterion and that is being treated by the IP under study and is not the development of new or progression of existing metastasis to the tumour under study). Malignant tumours that – as part of normal, if rare, progression – undergo transformation (e.g., Richter's transformation of B cell chronic lymphocytic leukaemia into diffuse large B cell lymphoma) should not be considered a new malignant tumour.

Life threatening

‘Life-threatening’ means that the participant was at immediate risk of death from the AE as it occurred or it is suspected that use or continued use of the product would result in the participant’s death. ‘Life-threatening’ does not mean that had an AE occurred in a more severe form it might have caused death (e.g. hepatitis that resolved without hepatic failure).

Hospitalisation

Outpatient treatment in an emergency room is not in itself a serious AE, although the reasons for it may be (e.g. bronchospasm, laryngeal oedema). Hospital admissions and/or surgical operations planned before or during a study are not considered AEs if the illness or disease existed before the participant was enrolled in the study, provided that it did not deteriorate in an unexpected way during the study.

Important medical event or medical treatment

Medical and scientific judgement should be exercised in deciding whether a case is serious in situations where important medical events may not be immediately life threatening or result in death, hospitalisation, disability or incapacity but may jeopardise the participant or may require medical treatment to prevent one or more outcomes listed in the definition of serious. These should usually be considered as serious.

Simply stopping the suspect drug does not mean that it is an important medical event; medical judgement must be used.

- Angioedema not severe enough to require intubation but requiring iv hydrocortisone treatment
- Hepatotoxicity caused by paracetamol (acetaminophen) overdose requiring treatment with N-acetylcysteine
- Intensive treatment in an emergency room or at home for allergic bronchospasm
- Blood dyscrasias (e.g. neutropenia or anaemia requiring blood transfusion, etc.) or convulsions that do not result in hospitalisation
- Development of drug dependency or drug abuse.

Intensity rating scale:

The grading scales found in the revised National Cancer Institute CTCAE latest version will be utilised for all events with an assigned CTCAE grading. For those events without assigned CTCAE grades, the recommendation in the CTCAE criteria that converts mild, moderate and severe events into CTCAE grades should be used. A copy of the CTCAE can be downloaded from the Cancer Therapy Evaluation Program website (<http://ctep.cancer.gov>). The applicable version of CTCAE should be described clearly.

B 3 A Guide to Interpreting the Causality Question

When making an assessment of causality consider the following factors when deciding if there is a ‘reasonable possibility’ that an AE may have been caused by the drug.

- Time Course. Exposure to suspect drug. Has the participant actually received the suspect drug? Did the AE occur in a reasonable temporal relationship to the administration of the suspect drug?
- Consistency with known drug profile. Was the AE consistent with the previous knowledge of the suspect drug (pharmacology and toxicology) or drugs of the same pharmacological class? Or could the AE be anticipated from its pharmacological properties?
- De-challenge experience. Did the AE resolve or improve on stopping or reducing the dose of the suspect drug?
- No alternative cause. The AE cannot be reasonably explained by another aetiology such as the underlying disease, other drugs, other host or environmental factors.
- Re-challenge experience. Did the AE reoccur if the suspected drug was reintroduced after having been stopped?
- Laboratory tests. A specific laboratory investigation (if performed) has confirmed the relationship.

In difficult cases, other factors could be considered such as:

- Is this a recognised feature of overdose of the drug?
- Is there a known mechanism?

Causality of ‘related’ is made if following a review of the relevant data, there is evidence for a ‘reasonable possibility’ of a causal relationship for the individual case. The expression ‘reasonable possibility’ of a causal relationship is meant to convey, in general, that there are facts (evidence) or arguments to suggest a causal relationship.

The causality assessment is performed based on the available data including enough

information to make an informed judgment. With no available facts or arguments to suggest a causal relationship, the event(s) will be assessed as ‘not related’.

Causal relationship in cases where the disease under study has deteriorated due to lack of effect should be classified as no reasonable possibility.

B 4 Medication Error

For the purposes of this clinical study a medication error is an unintended failure or mistake in the treatment process for a Redx study drug that either causes harm to the participant or has the potential to cause harm to the participant.

A medication error is not lack of efficacy of the drug, but rather a human or process related failure while the drug is in control of the study site staff or participant.

Medication error includes situations where an error:

- occurred
- was identified and intercepted before the participant received the drug
- did not occur, but circumstances were recognised that could have led to an error

Examples of events to be reported in clinical studies as medication errors:

- Drug name confusion
- Dispensing error e.g. medication prepared incorrectly, even if it was not actually given to the participant
- Drug not administered as indicated, for example, wrong route or wrong site of administration
- Drug not taken as indicated e.g. tablet dissolved in water when it should be taken as a solid tablet, tablet taken with food when it should be taken fasted.
- Drug not stored as instructed e.g. kept in the fridge when it should be at room temperature
- Wrong participant received the medication
- Wrong drug administered to participant.

Examples of events that **do not** require reporting as medication errors in clinical studies:

- Participant accidentally missed drug dose(s) e.g. forgot to take medication
- Accidental overdose (will be captured as an overdose)
- Participant failed to return unused medication or empty packaging

- Errors related to background and rescue medication, or standard of care medication in open-label studies.

Medication errors are not regarded as AEs, but AEs may occur as a consequence of the medication error.

